14.3. Analysis Populations

Safety Population:

All subjects who were administered any test article excluding subjects who drop out prior to administering any test article. At least one observation should be recorded.

Per-Protocol Population:

All subjects who have successfully completed all visits and did not substantially deviate from the protocol as determined by the trial cohort review committee prior to database hard lock (Per-Protocol Population). Justification of excluding subjects with protocol deviations in the per-protocol population set will be documented in a memo to file.

Intent-to-Treat (ITT) Population:

All randomized subjects regardless of actual treatment and subsequent withdrawal from study or deviation from protocol. At least one observation should be recorded.

14.4. Level of Statistical Significance

All planned analysis for this study will be conducted with an overall type I error rate of 5%.

14.5. Primary Analysis

Primary efficacy analysis:

The CLUE handling score will be analyzed using a linear mixed model. The model will include the experimental design factors: sequence of lens wear, lens wearing period and lens type as fixed effects. Site and subject nested in site will be included as random effects. Age and gender will be included as fixed covariates when appropriate. The covariance between residual errors from the same subject across lens wearing periods will be selected based on the finite-sample corrected Akaike's Information Criterion (Keselman et al. 1998²). Covariance structures considered may include: Homogenous compound symmetry (CS) and Unstructured covariance structure (UN). The structure that returns the lowest Akaike Information Criteria Corrected (AICC) will be selected as the structure that best fit the data.

Comparisons between each Test lens and Control lens will be carried out using 95% confidence intervals constructed of least-square means (LSM) differences (Test minus Control) from the linear mixed models. Non-inferiority will be concluded if the lower confidence limit is greater than -5 points.

In all models, the Kenward and Roger method (Kenward and Roger, 1997) will be used for the calculation of the denominator of degrees of freedom.

14.6. Secondary Analysis

Secondary efficacy analysis:

The secondary analysis will be conducted using the same method as the primary analysis.

14.7. Other Exploratory Analyses

Not Applicable.

14.8. Interim Analysis

Not Applicable.

14.9. Procedure for Handling Missing Data and Drop-Outs

Missing or spurious values will not be imputed. The count of missing values will be included in the summary tables and listings.

Subject dropout is expected to be one of the main reasons of missing data in this clinical trial. Past clinical trials don't provide the evidence that subject dropout is systematic or not-at-random. To evaluate the impact of missing data, sensitivity analysis will be conducted using multiple imputation methods if the proportion of subject dropout is greater than the 15%. The SAS/STAT procedures PROC MI and PROC MIANALYZE will be utilized with a parametric regression method used to make at least 5 imputations.

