4.3. Enrollment Target and Study Duration

Approximately 100 subjects will be enrolled in the study with 80 targeted to complete the cohort. All subjects will have at least -1.00 D to -1.50 D of refractive cylinder in both eyes. The study will take place at several clinical sites and have two study visits per subject.

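### Section 14.9 lets the missing-data sensitivity analysis run on 5 imputations with no fixed seed, so its reading against -5 can change through simulation noise alone; the primary verdict is unaffected

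*Combined protocol and SAP*

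**What the plan says.** Section 14.9 separates the main analysis from the sensitivity analysis. For the main analysis, "Missing or spurious values will not be imputed". To gauge the effect of missing data, "sensitivity analysis will be conducted using multiple imputation methods if the proportion of subject dropout is greater than the 15" per cent. The tools are PROC MI and PROC MIANALYZE, with a "parametric regression method used to make at least 5 imputations". The section gives no seed, no target for Monte Carlo error, no rule for raising the number of imputations and no analysis population.

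Four other sections bear on the point:

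- **Section 4.3:** "Approximately 100 subjects will be enrolled in the study with 80 targeted to complete the cohort".
- **Section 14.5:** the primary decision comes from the mixed-model 95% interval. "Non-inferiority will be concluded if the lower confidence limit is greater than -5 points".
- **Section 14.1:** all analyses are placed on the per-protocol population.
- **Section 14.3:** the per-protocol population is limited to subjects who completed all visits. An ITT population (all randomised subjects, with at least one observation recorded) is defined, but no analysis is assigned to it.

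**The concern.** Multiple imputation draws random numbers, so its interval varies from one seed to the next, and the variation shrinks as imputations are added. An analyst who uses 5 complies fully with Section 14.9.

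The purpose of the analysis is to show whether the non-inferiority finding survives dropout. The natural way to read it is to set its lower limit beside the same -5 margin. If that limit moves by around half a point between seeds, the check can appear to support or undermine the primary result by chance. With no seed fixed before unmasking, a rerun need not reproduce the first answer, and the plan does not rule out choosing among runs.

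**Working it through.** **1. Is the analysis likely to run?** Planned loss is (100 - 80)/100 = 20%, against a 15% trigger. If each of 100 subjects drops out with probability 0.20, the binomial chance of 16 or more dropouts is 0.87.

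**2. What SD applies?** The documents state no figure for seed-to-seed variation. The nearest figure is the Section 14.2 sample-size table (116, 87, 180, 135), whose SD is not given. With n = (z_alpha + z_beta)^2 x 2 SD^2 (1 - rho)/(5 + diff)^2 and 80% power:

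- SD 20 (the CLUE population value in Section 2.2), one-sided 0.025: 101, 76, 157, 118. This does not match.
- SD 21.26, one-sided 0.025: 113.5, 85.1, 177.4, 133.0. Adding the small-sample term 1.96^2/2 = 1.9 gives 115.4, 87.0, 179.3, 134.9, which matches to within rounding.
- SD 24.0, one-sided 0.05: about 114, 86, 179, 134. This fits about equally well.

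The SD is therefore an assumption, and the range 20 to 24 is used. The correlations (0.6, 0.7) and true differences (0, -1) are those of Section 14.2.

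**3. One case by hand.** Take SD 21.26, rho 0.7, true difference 0, 100 randomised, and 20 lost after visit 1 (two of five lenses scored, as Section 5.1 implies). Simulation puts the fraction of missing information (FMI) at about 0.165.

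- Complete-data variance: U = 2 x 21.26^2 x 0.3/100 = 2.71.
- Total variance: T = U/(1 - 0.165) = 3.25, so SE = 1.80.
- Between-imputation variance: B = 0.165 x 3.25 = 0.536.
- Seed SD of the pooled estimate, sqrt(B/m): 0.327 at m = 5; 0.104 at m = 50.
- Seed SD of the half-width, 1.97 x (1 + 1/m) x B x sqrt(2/(m - 1))/(2 sqrt(T)): 0.249 at m = 5; 0.060 at m = 50.
- Combined: sqrt(0.327^2 + 0.249^2) = 0.41 at m = 5; sqrt(0.104^2 + 0.060^2) = 0.12 at m = 50.

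The lower limit averages -1.97 x 1.80 = -3.55, which is 0.80 SE above -5. Its density at -5 is 0.289/1.80 = 0.160 per point. For small noise s, the chance that two seeds fall on opposite sides of -5 is about (2/sqrt(pi)) x s x density:

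- m = 5: 1.128 x 0.41 x 0.160 = 7.4%
- m = 50: 1.128 x 0.12 x 0.160 = 2.2%

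This is slightly low at m = 5 because it ignores the varying degrees of freedom.

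**4. Simulation.** A 5x5 Williams crossover was simulated with regression imputation, Rubin's rules with Barnard-Rubin degrees of freedom, and independent sets of imputations. Results for 100 randomised, 20 dropouts and SD 21.26:

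| rho, true difference | m | SD of lower limit | Disagree, per comparison | Disagree, both primaries jointly |
|---|---|---|---|---|
| 0.6, 0 | 5 | 0.51 | 10.9% | 12.2% |
| 0.6, 0 | 20 | 0.22 | 4.8% | 5.6% |
| 0.6, 0 | 100 | 0.08 | 2.1% | 2.4% |
| 0.7, 0 | 5 | 0.45 | 8.6% | 11.1% |
| 0.7, 0 | 20 | 0.19 | 4.0% | 5.2% |
| 0.7, 0 | 100 | 0.07 | 1.5% | 1.8% |
| 0.7, -1 | 5 | 0.45 | 11.0% | 11.1% |
| 0.7, -1 | 20 | 0.19 | 5.0% | 5.2% |
| 0.7, -1 | 100 | 0.07 | 2.8% | 3.4% |

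Across SD 20 to 24 and 16 to 20 dropouts, the m = 5 rates were 7 to 12% per comparison and 8 to 14% jointly. At m = 50 both were 2 to 4%. A separate, smaller simulation (100 trials per scenario, rho 0.7, difference 0, 20 lost after visit 1) gave 6 to 10% at m = 5 and 1 to 3% at m = 50. A direct Rubin's-rules calculation at FMI 0.165 gave 10.1% at 65% power and 8.0% at 80% power for m = 5, and 2.8% and 2.1% for m = 50.

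**The case against.** Several stronger readings are tempting, and the documents do not support them.

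- **That the trial's non-inferiority verdict could flip with the seed.** It cannot. Section 14.5 takes the verdict from a mixed model without imputation, and Section 14.9 gives the imputed analysis no pass/fail rule. Setting its limit against -5 is how a reader would use it, not a decision the plan assigns to it.
- **That the trigger is bound to be met.** The 80 is a completion target out of approximately 100. Those enrolled may include screen failures, since Section 5.1 randomises only after eligibility is confirmed. Sections 5.2 and 8.2 also allow discontinued subjects to be replaced.
- **That 5 imputations will be used.** Five is a floor, and 50 or 100 already comply.
- **That one trial in ten is a fixed rate.** It lies towards the unfavourable end of an assumption-dependent range. Clear results do not flip. If the test lens is truly 2 points better (16 dropouts), the rate is 1.7% per comparison and 2.9% jointly. With 136 enrolled and 21 dropouts it is 5.6% per comparison. With 30% dropout it is 14%. Part of the height comes from 80 completers being below every row of the sample-size table (minimum 87), which puts results near the margin.

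The strongest remaining objection is that, read literally, Sections 14.1 and 14.3 confine every analysis to completers. In that set there is no dropout to impute, and the number of imputations would hardly matter. That is right, but it shows a second gap in Section 14.9 rather than removing the first: the analysis can do its job only on a population that contains the dropouts.

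**Conclusion.** The point holds as a minor one. Section 14.9 permits a sensitivity analysis whose lower limit varies between seeds with an SD of about 0.35 to 0.6 CLUE points. Two seeds would disagree about -5 in roughly 6 to 12% of trials per comparison at 5 imputations, against about 1 to 4% at 50. These are averages over trials in which the analysis is run, and the disagreements are concentrated where the limit lies close to -5, which is where a robustness check is most needed.

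The figures assume an SD of 20 to 24, the Section 14.2 correlations and true differences, 16 to 20 dropouts among 100 mostly lost between the visits, and imputation on a population that includes those dropouts. The documents settle neither the SD nor the timing of dropout.

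**What to change.** In Section 14.9, replace the floor of 5 with at least 50 imputations, preferably 100, and a seed specified before unmasking. Both parts are needed: a seed makes the result reproducible but does not reduce the noise, and more imputations reduce the noise but do not prevent a choice among runs.

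In the same sentence, state that this sensitivity analysis is run on the ITT population of Section 14.3 (randomised subjects with at least one observation), as an exception to the per-protocol rule in Section 14.1.

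The cost is one changed number, one seed and one sentence on population, plus seconds of computing. No extra subjects or data are needed, and the primary analysis is unchanged.

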14.10. Procedure for Reporting Deviations from Statistical Plan

The analysis will be conducted according to that specified in above sections. There are no known reasons for which it is planned to deviate from these analysis methods. If for any reason a change is made, the change will be documented in the study report along with a justification for the change.

15. DATA HANDLING AND RECORD KEEPING/ARCHIVING

15.1. Electronic Case Report Form/Data Collection

The data for this study will be captured on electronic case report forms (eCRFs) using Bioclinica Express version 5.5 EDC system). An authorized data originator will enter study data into the eCRFs using the EDC system. Data collected on equipment that is not captured in EDC will be formatted to the specification of the JJVC database manager and sent to JJVC for analysis.

The clinical data will be recorded on dedicated eCRFs specifically designed to match the study procedures for each visit. Once completed, the eCRFs will be reviewed for accuracy and completeness and signed by the Investigator. The sponsor or sponsor's representatives will be authorized to gain access to the subject recordation for the purposes of monitoring and auditing the study.

Edit checks, electronic queries, and audit trails are built into the system to ensure accurate and complete data collection. Data will be transmitted from the clinical site to a secure central database as forms are completed or updated, ensuring information accuracy, security, and confidentiality. After the final database lock, the Investigator will be provided with Individual Patient Profiles (IPP) including the full audit trail on electronic media in PDF format for all of the study data. The IPP must be retained in the study files as a certified copy of the source data for the study.

The content and structure of the eCRFs are compliant with ISO14155:2011.

15.2. Subject Record

At a minimum, subject record should be available for the following:

- subject identification
- eligibility
- study identification
- study discussion
- provision of and date of informed consent
- visit dates
- results of safety and efficacy parameters as required by the protocol
- a record of all adverse events
- follow-up of adverse events
- medical history and concomitant medication
- test article receipt/dispensing/return records
- date of study completion
- reason for early discontinuation of test article or withdrawal from the study, if applicable

The subject record is the eCRF or an external record. The author of an entry in the subject record must be identifiable. The first point of entry is considered to be the source record.

Adverse event notes must be reviewed and initialed by the Investigator.

16. DATA MANAGEMENT

16.1. Access to Source Data/Document

The Investigator/Institution will permit trial-related monitoring, audits, IEC/IRB review and regulatory inspection(s) by providing direct access to source data/documents. Should the clinical site be contacted for an audit by an IEC/IRB or regulatory authority, JJVC must be contacted and notified in writing within 24 hours.

16.2. Confidentiality of Information

Information concerning the investigational product and patent application processes, scientific data or other pertinent information is confidential and remains the property of JJVC. The Investigator may use this information for the purposes of the study only. It is understood by the Investigator that JJVC will use information developed in this clinical study in connection with the development of the investigational product and therefore may disclose it as required to other clinical investigators and to regulatory agencies. In order to allow the use of the information derived from this clinical study, the Investigator understands that he/she has an obligation to provide complete test results and all data developed during this study to the Sponsor.

16.3. Data Quality Assurance

Steps will be taken to ensure the accuracy and reliability of data, include the selection of qualified investigators and appropriate clinical sites and review of protocol procedures with the Principal Investigator. The Principal Investigator, in turn, must ensure that all Sub-Investigators and clinical site personnel are familiar with the protocol and all study-specific procedures and have appropriate knowledge of the study article.

Training on case report form completion will be provided to clinical site personnel before the start of the study. The Sponsor will review case report forms for accuracy and completeness remotely during the conduct of the study, during monitoring visits, and after transmission to data management. Any data discrepancies will be resolved with the Investigator or designee, as appropriate.

Quality Assurance representatives from JJVC may visit clinical sites to review data produced during the study and to access compliance with applicable regulations pertaining to the conduct of clinical trials. The clinical sites will provide direct access to study-related source data/documents and reports for the purpose of monitoring and auditing by JJVC and for inspection by local and regulatory authorities.

17. MONITORING

The study monitors will maintain close contact with the Principal Investigator and the Investigator's designated clinical site personnel. The monitor's responsibilities will include:

- Ensuring that the investigation is being conducted according to the protocol, any subsequent amendments, and regulatory requirements are maintained
- Ensuring the rights and wellbeing of subjects are protected
- Ensuring adequate resources, including facilities, laboratories, equipment, and qualified clinical site personnel
- Ensuring that protocol deviations are documented with corrective action plans, as applicable
- Ensuring that the clinical site has sufficient test article and supplies
- Clarifying questions regarding the study
- Resolving study issues or problems that may arise

- Reviewing of study records and source documentation verification in accordance with the monitoring plan

18. ETHICAL AND REGULATORY ASPECTS

18.1. Study-Specific Design Considerations

Potential subjects will be fully informed of the risks and requirements of the study and, during the study, subjects will be given any new information that may affect their decision to continue participation. Subjects will be told that their consent to participate in the study is voluntary and may be withdrawn at any time with no reason given and without penalty or loss of benefits to which they would otherwise be entitled. Only subjects who are fully able to understand the risks, benefits, and potential adverse events of the study, and provide their consent voluntarily will be enrolled.

18.2. Investigator Responsibility

The Principal Investigator is responsible for ensuring that the clinical study is performed in accordance with the signed agreement, the investigational plan, Section 4 of the ICH E6 guidelines on Good Clinical Practice (GCP), and applicable regulatory requirements. GCP is an international ethical and scientific quality standard for designing, conducting, recording, and reporting studies that involve the participation of human subjects. Compliance with this standard provides public assurance that the rights, safety, and well-being of study subjects are protected, consistent with the principles of the Declaration of Helsinki 64th WMA General Assembly 2013 and that the clinical study data are credible. The Investigator must maintain clinical study files in accordance with Section 8 of the ICH E6 guidelines on Good Clinical Practice (GCP), and applicable regulatory requirements.

18.3. Independent Ethics Committee or Institutional Review Board (IEC/IRB)

Before the start of the study, the Investigator (or Sponsor when applicable) will provide the IEC/IRB with current and complete copies of the following documents (where applicable):

- Final protocol and, if applicable, amendments
- Sponsor-approved informed consent form (and any other written materials to be provided to the subjects)
- Investigator's Brochure (or equivalent information) and amendments
- Sponsor-approved subject recruitment materials
- Information on compensation for study-related injuries or payment to subjects for participation in the study
- Investigator's curriculum vitae, clinical licenses, or equivalent information (unless not required, as documented by IEC/IRB)
- Information regarding funding, name of the Sponsor, institutional affiliations, other potential conflicts of interest, and incentives for subjects
- Any other documents that the IEC/IRB requests to fulfill its obligation

This study will be undertaken only after IEC/IRB has given full approval of the final protocol, amendments (if any), the informed consent form, applicable recruiting materials,

and subject compensation programs, and the Sponsor has received a copy of this approval. This approval letter must be dated and must clearly identify the documents being approved.

During the study the Investigator (or Sponsor when applicable) will send the following documents to the IEC/IRB for their review and approval, where appropriate:

- Protocol amendments
- Revision(s) to informed consent form and any other written materials to be provided to subjects
- If applicable, new or revised subject recruitment materials approved by the Sponsor
- Revisions to compensation for study-related injuries or payment to subjects for participation in the study
- Investigator's Brochure amendments or new edition(s)
- Summaries of the status of the study (at least annually or at intervals stipulated in guidelines of the IEC/IRB)
- Reports of adverse events that are serious, unanticipated, and associated with the test articles, according to the IRB's requirements
- New information that may adversely affect the safety of the subjects or the conduct of the study
- Major protocol deviations as required by the IEC/IRB
- Report of deaths of subjects under the Investigator's care
- Notification if a new Investigator is responsible for the study at the clinical site
- Any other requirements of the IEC/IRB

For protocol amendments that increase subject risk, the amendment and applicable informed consent form revisions must be submitted promptly to the IEC/IRB for review and approval before implementation of the change(s).

At least once a year, the IEC/IRB will review and reapprove this clinical study. This request should be documented in writing.

At the end of the study, the Investigator (or Sponsor where required) will notify the IEC/IRB about the study completion. Documentation of this notification must be retained at the clinical site and a copy provided to the CRO or Sponsor as applicable.

18.4. Informed Consent

Each subject must give written consent according to local requirements after the nature of the study has been fully explained. The consent form must be signed before performance of any study-related activity. The consent form that is used must be approved by both the Sponsor and by the reviewing IEC/IRB. The informed consent is in accordance with principles that originated in the Declaration of Helsinki, current ICH and GCP guidelines, applicable regulatory requirements, and Sponsor policy.

Before entry into the study, the Investigator or an authorized member of the clinical site personnel must explain to potential subject the aims, methods, reasonably anticipated benefits, and potential hazards of the study, and any discomfort it may entail. Subjects will be

informed that their participation is voluntary and that they may withdraw consent to participate at any time.

The subject will be given sufficient time to read the informed consent form and the opportunity to ask questions. After this explanation and before entry into the study, consent should be appropriately recorded by means of the subject's dated signature. After having obtained the consent, a copy of the informed consent form must be given to the subject.

